#### 12.1.2.7 Adverse Events

Record all AEs including SSIs. Use the AE form as described in *Section 13: Device Deficiencies and Adverse Events*.

#### 12.1.2.8 Device Deficiencies

Record device deficiencies if observed. Use the Device Deficiency Form as described in *Section 13: Device Deficiencies and Adverse Events*.

## 12.1.3 1-Day Postoperative Visit (Visit 1 – Day 1, Unilateral)

#### 12.1.3.1 Ocular and Non-ocular Concomitant Medication

Record changes in ocular and non-ocular concomitant medications.

**Document:** TDOC-0050176 Version: 2.0; Effective; CURRENT

Status: Effective Page 42 of 75

## 12.1.3.2 Intraocular Pressure (IOP)

Measure IOP using Goldmann or other applanation method. For each subject, the same instrument type should be used for all measurements in the study.

## 12.1.3.4 Slit-lamp Examination

Examine the anterior segment of the eye, including the eyelid, sclera, conjunctiva, cornea, iris, and natural crystalline lens. Record all new clinical observations and note the clinical significance of each observation.

**NOTE:** Certain pathologies may become apparent after cataract extraction and IOL implantation. In these instances, the preoperative pathology status should be updated.

## 12.1.3.5 Inflammatory Signs

Grade inflammatory signs including cells and flares, and corneal edema. Refer to MOP (*Inflammatory Signs Grading*) for details including grading scale.

#### 12.1.3.6 Adverse Events

Record all AEs including SSIs. Use the AE form as described in *Section 13: Device Deficiencies and Adverse Events*.

## 12.1.4 1-Week Postoperative Visit (Visit 2 – 7 +/- 2 Days, Unilateral)

#### 12.1.4.1 Ocular and Non-ocular Concomitant Medication

Record changes in ocular and non-ocular concomitant medications.

## 12.1.4.2 Visual Acuity (UCDVA and BCDVA) Testing

Perform Uncorrected Distance Visual Acuity (UCDVA) testing and Best Corrected Distance Visual Acuity (BCDVA) testing with study specified equipment. Refer to MOP for further instruction.

Ensure UCDVA and BCDVA testing precedes IOP measurement, the administration of eye drops to dilate or anesthetize the eyes, or any examination requiring contact with the eye.

Document: TDOC-0050176 Version: 2.0; Effective; CURRENT

Status: Effective Page 43 of 75

NOTE: Lighting conditions must be measured and recorded prior to VA testing.

## 12.1.4.3 Intraocular Pressure (IOP)

Measure IOP using Goldmann or other applanation method. For each subject, the same instrument type should be used for all measurements in the study.

## 12.1.4.5 Slit-lamp Examination

Examine the anterior segment of the eye, including the eyelid, sclera, conjunctiva, cornea, iris, and natural crystalline lens. Record all new clinical observations and note the clinical significance of each observation.

**NOTE:** Certain pathologies may become apparent after cataract extraction and IOL implantation. In these instances, the preoperative pathology status should be updated.

## 12.1.4.6 Inflammatory Signs

Grade inflammatory signs including cells and flares, and corneal edema. Refer to MOP (*Inflammatory Signs Grading*) for details including grading scale.

#### 12.1.4.7 Adverse Events

Record all AEs including SSIs. Use the AE form as described in *Section 13: Device Deficiencies and Adverse Events*.

# 12.1.5 3-Month Postoperative Visit (Visit 3 – 90 +/- 14 Days, Unilateral)

#### 12.1.5.1 Ocular and Non-ocular Concomitant Medication

Record changes in ocular and non-ocular concomitant medications.

**Document:** TDOC-0050176 **Version:** 2.0; Effective; CURRENT

Status: Effective Page 44 of 75

## 12.1.5.2 Visual Acuity (UCDVA and BCDVA) Testing

Perform Uncorrected Distance Visual Acuity (UCDVA) testing and Best Corrected Distance Visual Acuity (BCDVA) testing with study specified equipment. Refer to MOP for further instruction.

Ensure UCDVA and BCDVA testing precedes IOP measurement, the administration of eye drops to dilate or anesthetize the eyes, or any examination requiring contact with the eye.

*NOTE:* Lighting conditions must be measured and recorded prior to VA testing.

## 12.1.5.3 Intraocular Pressure (IOP)

Measure IOP using Goldmann or other applanation method. For each subject, the same instrument type should be used for all measurements in the study.

## 12.1.5.4 Specular Microscopy

Utilize a commercially available specular microscope (Konan microscope) to photograph the corneal endothelial cells as per the instructions provided by the Reading Center; the images will then be transferred to the Reading Center for analysis.

**NOTE:** If the subject has been dismissed prior to assessment of image quality (not recommended) and images are of poor quality, the subject will be asked to return and the assessment repeated.

## 12.1.5.5 Slit-lamp Examination

Examine the anterior segment of the eye, including the eyelid, sclera, conjunctiva, cornea, iris, and natural crystalline lens. Record all new clinical observations and note the clinical significance of each observation.

**NOTE:** Certain pathologies may become apparent after cataract extraction and IOL implantation. In these instances, the preoperative pathology status should be updated.

## 12.1.5.6 Inflammatory Signs

Grade inflammatory signs including cells and flares, and corneal edema. Refer to MOP (*Inflammatory Signs Grading*) for details including grading scale.

Document: TDOC-0050176 Version: 2.0; Effective; CURRENT

Status: Effective Page 45 of 75

#### 12.1.5.7 Dilated Fundus Examination

Perform a dilated fundus examination (indirect and direct ophthalmoscopy). Record diameter of dilated pupil. Record all preoperative baseline clinical observations with consideration given to the inclusion and exclusion criteria (Refer to *Section 10: Subject Population*) and note clinical significance.

*NOTE:* Certain pathologies may become apparent after cataract extraction and IOL implantation. In these instances, the preoperative pathology status should be updated.

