## 12.1.1.11 Slit-lamp Examination

Examine the anterior segment of the eye, including the eyelid, sclera, conjunctiva, cornea, iris, and natural crystalline lens. Record all preoperative baseline clinical observations and the clinical significance of each observation. Give consideration to Inclusion/Exclusion criteria (refer to *Section 10: Subject Population*).

*NOTE:* Certain pathologies may become apparent after cataract extraction and IOL implantation. In these instances, the preoperative pathology status should be updated.

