5.1 Safety Endpoints

The safety endpoints are:

- Adverse events (including Secondary Surgical Interventions (SSIs))
- Slit-lamp examination findings (clinical observations)
- Anterior chamber cells
- Anterior chamber flare
- Corneal edema
- Endothelial cell count
- Dilated fundus examination findings (clinical observations)
- Best corrected distant visual acuity (BCDVA)
- Intraocular pressure (IOP)
- Problems during surgery
- IOL placement
- Device deficiencies

Analysis for the anterior chamber cells, anterior chamber flare and endothelial cell counts will be presented in the performance analysis section.

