5.3.4 Dilated Fundus Examination

Fundus examination will be performed at pre-operative Visit 0 and post-operative Visit 3.

Number and percentage of fundus exam findings will be summarized for each visit by procedure. A listing of fundus exam findings will be provided for each visit by procedure.

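### The Month 3 fundus examination, the only scheduled one after surgery, carries the Visit 0 recording instruction and does not ask for new or changed findings

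*Protocol*

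**What the plan says.** Dilated fundus examination is a listed safety endpoint (Protocol 8.4.2 and 15.7; SAP 5.1). The Protocol section 6 schedule and the SAP appendix schedule place it at two visits, and SAP 5.3.4 confirms this: "Fundus examination will be performed at pre-operative Visit 0 and post-operative Visit 3".

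For the Visit 3 examination, Protocol 12.1.5.7 instructs: "Record all preoperative baseline clinical observations with consideration given to the inclusion and exclusion criteria". It also asks for the dilated pupil diameter and the clinical significance of what is recorded. A note adds that some pathology may become visible only once the cataract is out, and continues: "In these instances, the preoperative pathology status should be updated".

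The slit-lamp sections change between visits. At Visit 0 (12.1.1.11) the text is "Record all preoperative baseline clinical observations and the clinical significance of each observation". At Visit 3 (12.1.5.5) it is "Record all new clinical observations and note the clinical significance of each observation", and Visits 1 and 2 use the same wording.

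The planned fundus analysis is in SAP 5.3.4: "Number and percentage of fundus exam findings will be summarized for each visit by procedure", and "A listing of fundus exam findings will be provided for each visit by procedure". No category for new, worsened or changed findings is defined.

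**The concern.** Three months after surgery, eligibility has long been settled. An instruction to record preoperative observations against the entry criteria has no purpose at that visit. What a safety endpoint needs there is what the examiner sees now and whether it differs from Visit 0, and the section asks for neither.

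The fundus table is meant to be a systematic record, collected the same way in every eye and separate from what investigators choose to report as adverse events. If some sites re-enter baseline disease, others enter only new disease and others enter everything, the Visit 3 counts by arm do not measure one thing. Findings that an investigator does not judge clinically relevant have no other required place to go.

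**Working it through.** No figure in the plan is at issue, so the check is a comparison of texts.

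**1. Is the wording a carry-over?** Protocol 12.1.1.14 (fundus, Visit 0) and 12.1.5.7 (fundus, Visit 3) use the same recording sentence and the same note. The slit-lamp sections start from similar baseline wording at Visit 0 and switch to new observations at Visits 1, 2 and 3. The fundus text alone was not switched.

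**2. Does another scheduled examination make up for it?** No. The section 6 schedule marks the fundus at Visit 0 and Visit 3 and leaves the 6-month safety visit blank. Sections 12.4 and 12.6 recommend a fundus examination at unscheduled and early-exit visits, but a subject who simply completes the study has neither.

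**3. What happens to each kind of Visit 3 finding if the text is followed literally?**

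| Finding at Visit 3 | Requested by 12.1.5.7? | Other route |
|---|---|---|
| Present at Visit 0, unchanged | Yes | None needed |
| Present at Visit 0, worsened | Baseline state yes, the change no | AE if the investigator judges it clinically relevant (13.2) |
| New, judged clinically relevant | No | AE (12.1.5.8, 13.2) |
| New, not judged clinically relevant | No | None specified |
| First visible after surgery, assigned to baseline | Moved to preoperative status by the note | Not an AE (13.3) and not treatment-emergent unless it worsened (SAP 5.3.1) |

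The last row is right for disease that the cataract had hidden. It is wrong for disease that arose after surgery, and the section specifies no field that records how that decision was made.

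**4. Does the SAP repair it?** Not fully. Counts per visit show only the net difference between Visit 0 and Visit 3: a finding that resolves in one eye offsets one that appears in another. The listings allow an eye-by-eye comparison, but only of what was entered. By contrast, SAP 5.3.5 and 5.3.6 specify change from baseline for BCDVA and IOP.

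**5. How many records are affected?** One scheduled postoperative fundus record per eye: 3 × 59 = 177 planned, and at least 3 × 53 = 159 expected at Month 3 (Protocol 9.1). The documents give no rate of new fundus findings, so the number lost cannot be estimated from them.

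**The case against.** The strongest reply is that new retinal harm has a separate route to the report. Protocol 13.2 has the investigator review changes in every examined ocular parameter and report clinically relevant untoward ones as AEs, whatever the cause. Section 12.1.5.8 repeats AE recording at Visit 3. SAP 5.3.1 counts both new events and worsening of old ones as treatment-emergent, with ocular and serious AEs as classes, and SAP 5.3 reports by procedure group. BCDVA change from baseline adds a partial functional check. This stands. It depends, however, on the opinion of an investigator who, as surgeon, is not masked (Protocol 7.2 and 13.4), and it does not cover findings judged not relevant or reassigned to baseline.

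Second, Protocol 14.1 requires the results of protocol testing to be in the source and required examinations to be on the eCRF, and SAP 5.3.4 tabulates and lists Visit 3 findings. Many examiners will enter what they see. This also stands, and it limits the consequence to incomplete or inconsistent recording.

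Third, Protocol 12.1 describes assessments only in general and leaves detail to the MOP. Neither the MOP nor the eCRF was available, and either may state what is captured. Section 12.1.5.7 does not itself point to the MOP, however, and the protocol sentence would still need to agree with it.

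Fourth, per-visit counts with listings are a legitimate descriptive plan: slit-lamp findings are handled the same way (SAP 5.3.2) and there are no safety hypotheses (SAP 5.2). Accepted. The SAP format alone would not be a fault. It matters here because the entries that feed it are misdirected.

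A reader might go further and infer that the fundus endpoint cannot show new retinal harm by arm, or that its table would look the same before and after surgery whatever happened. The first and second replies rule that out.

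**Conclusion.** The Visit 3 fundus instruction is wrong as written. It is a drafting carry-over, but it sits in the only scheduled postoperative record of a listed safety endpoint, so it should be corrected. The supportable consequence is that Visit 3 fundus findings may be under-recorded or recorded inconsistently, and that the SAP 5.3.4 table is therefore unreliable for new findings. The AE tables remain a real but incomplete backstop.

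The instruction reaches 159 to 177 eyes. How many findings would be lost is unknown. The conclusion assumes that sites follow the protocol text and that the MOP and eCRF do not already override it. If they do ask for current findings with their status relative to Visit 0, what remains is a wording conflict to be reconciled.

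**What to change.** - **Protocol 12.1.5.7, recording sentence.** Replace it with an instruction to enter every fundus observation present at that visit, class each one as new, worsened or present at Visit 0, and give its clinical significance. Copying the slit-lamp sentence would not be enough: it asks only for new observations and so leaves no place for findings already present at Visit 0.
- **Protocol 12.1.5.7, note.** State that it applies only to pathology judged to pre-date surgery, and that the Visit 3 entry is kept when the preoperative status is updated.
- **SAP 5.3.4.** Add a count and percentage, by procedure, of eyes with fundus findings that are new or worsened since Visit 0.
- **MOP and eCRF.** Check that both agree with the revised text.

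The cost is a short protocol wording change, one eCRF flag and one table row. No examination is added, and sample size, power and significance level are unaffected.

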#### 12.1.5.8 Adverse Events

Record all AEs including SSIs. Use the AE form as described in *Section 13: Device Deficiencies and Adverse Events*.

## 12.1.6 Additional 6-Month Safety Follow-up Visit

Subjects who have completed the 3 month visit with an ECD count of less than 1500 cells/mm^2 and/or a decrease in ECD of 20% or more (in comparison to the screening visit value) at their 3 month visit, must return 3 months later for a 6 month safety follow-up visit.

The following safety assessments are to be performed at the 6-Month Safety Follow-up visit:

- A repeat ECD assessment
- Visual Acuity BCDVA
- Slit lamp examination corneal edema
- \_
- Any other assessment performed as standard of care at the site

Subject data from the additional safety assessments will be captured in the electronic database, accordingly.

## **12.2 Discontinued Subjects**

Discontinued subjects withdraw, or are withdrawn, from the study after 1) signing consent, 2) meeting the inclusion and exclusion criteria, and 3) having been randomized. Subjects signing consent, but withdrawing prior to randomization shall be considered a screen failure, and the failed entry criterion documented (eg, inclusion criterion 2, exclusion criterion 4). Refer to *Section 10 SUBJECT POPULATION*. Subjects randomized, but withdrawing prior to surgery shall be considered discontinued, and the reason for discontinuation documented (eg, discontinued due to withdrawal by subject).

Document: TDOC-0050176 Version: 2.0; Effective; CURRENT

Status: Effective Page 46 of 75

Subjects may discontinue study participation at any time and for any reason. Subjects may be discontinued from the study at any time if in the opinion of the PI or designated, qualified medical personnel, continued participation poses a health risk. Subject numbers from discontinued subjects will not be reissued. Discontinued subjects will not be replaced.

#### 12.3 Clinical Trial Termination

The study can be terminated at any time by the Sponsor. If the study is terminated, the Investigator and any regulatory authorities will be informed within 5 days of the decision. The Investigator will be responsible for informing the subjects and their Institutional Review Board (IRB) of the early termination of the trial. The Sponsor will be responsible for providing procedures to ensure protection of the subject interests.

#### 12.4 Unscheduled Visit

After signing ICF, if a subject requires a study eye visit that is not specified in the protocol, the visit is considered an Unscheduled Visit (UNSV). For the 6-Month Safety Follow-up Visit please refer to Section 12.1.6.

Study eye ocular examinations conducted by non-study personnel are not considered an UNSV. Also, Pre-planned, routine postoperative visits (eg, 1-month postoperative visit) are not considered unscheduled visits unless an AE (serious or non-serious) is reported and study personnel are involved in the conduct of the visit.

**NOTE:** Any AE (serious or non-serious) arising from a pre-planned, routine postoperative visit must be captured and reported as in accordance with Section 13: Device Deficiencies and Adverse Events regardless of study personnel involvement.

During an unscheduled visit, it is recommended that the following information be collected:

- Concomitant medications
- Visual acuity (UCDVA, BCDVA)
- Slit-lamp exam
- Conjunctival edema grading
- Wound leakage
- Fundus exam
- IOP

**Document:** TDOC-0050176 **Version:** 2.0; Effective; CURRENT

Status: Effective Page 47 of 75

Adverse events and device deficiencies

Activities undertaken during an UNSV should be collected in accordance with this protocol and the MOP. Data collected will be entered into EDC.

If the subject is discontinued at the unscheduled visit, all Early Exit procedures should be performed. Refer to *Section 6 SCHEDULE OF VISITS*. If an UNSV is required after the final study visit for safety purposes, the data will not be captured in EDC. Refer to *Section 13.5 Follow-Up of Safety Information*.

#### 12.5 Missed Visit

If a subject unavoidably misses a scheduled exam, he/she should be rescheduled within the same exam period. The Investigational site should show diligence in trying to schedule the subject for all exams. If a subject is unable to return for the final study visit, the Exit Form should be completed with the appropriate reason for discontinuation indicated.

#### 12.6 Early Exit Visit

If a subject exits from the study early (ie, does not complete the scheduled or planned study visits) complete the early exit form including the following recommended activities:

- UCDVA and BCDVA
- IOP
- Specular microscopy
- Slit-lamp examination
- Inflammatory signs
- · Dilated fundus exam
- Note AEs (including SSIs)
- Note changes to systemic and ocular concomitant medications

Document: TDOC-0050176 Version: 2.0; Effective; CURRENT

[figure not shown]
Status: Effective Page 48 of 75

#### 13 DEVICE DEFICIENCIES AND ADVERSE EVENTS

#### 13.1 General Information

An adverse event (AE) is any untoward medical occurrence, unintended disease or injury, or untoward clinical signs (including abnormal laboratory findings) in subjects, users, or other persons, whether or not related to the investigational product (test or control article). For subjects, this definition includes events related to the test article, the control article, or the procedures involved. For users or other persons, this definition is restricted to events related to the test article.

Figure 13–1 Categorization of All Adverse Events

[figure not shown]

Document: TDOC-0050176 Version: 2.0; Effective; CURRENT

Status: Effective Page 49 of 75

Effective Date: 18-Jul-2016

Figure 13-2 Categorization of All Serious Adverse Events

#### Serious Adverse Events

A serious adverse event is an AE that led to any of the following:

- Death.
- A serious deterioration in the health of the subject that either resulted in:
  - a. a life-threatening illness or injury.
    Note: Life-threatening means that the individual was at immediate risk of death from the event as it occurred, ie, it does not include an event which hypothetically might have caused death had it occurred in a more severe form.
  - b. any potentially sight-threatening event or permanent impairment to a body structure or a body function.

Print Date:

**Document:** TDOC-0050176 **Version:** 2.0; Effective; CURRENT

Status: Effective Page 50 of 75

c. in-patient hospitalization or prolonged hospitalization.

Note: Planned hospitalization for a pre-existing condition, without serious deterioration in health, is not considered a SAE. In general, hospitalization signifies that the individual remained at the hospital or emergency ward for observation and/or treatment (usually involving an overnight stay) that would not have been appropriate in the physician's office or an out-patient setting. Complications that occur during hospitalization are AEs. If a complication prolongs hospitalization or fulfills any other serious criteria, the event is serious. When in doubt as to whether "hospitalization" occurred, the event should be considered serious.

- d. a medical or surgical intervention to prevent a) or b)
- e. any indirect harm as a consequence of incorrect diagnostic test results when used within manufacturer's instructions for use.
- Fetal distress, fetal death, or a congenital abnormality or birth defect.

#### Specific Events Relevant to this Protocol

In addition to reporting all AEs (serious and non-serious) meeting the definitions, the Investigator must report any occurrence of the following as an SAE:

- Capsule injury
- Thermal burns of the eye
- Vitreous loss

A change in corneal endothelial cell count following phacoemulsification and posterior chamber IOL implantation in subjects with a more advanced cataract (ie, Grades NII-NIV via LOCSII scoring) is an event of special interest. A change in corneal endothelial cell count has been defined as an ECD count of less than 1500 cells/mm² and/or a decrease in ECD of 20% or more at the subjects 3 month visit. To further characterize changes in ECD from baseline, an AE must be reported for any subject who experiences a change as defined above. Adverse events for corneal endothelial cell loss may be considered serious based on the judgment of the investigator.

Any other potentially sight-threatening event may also be considered serious based on the judgment of the Investigator and should be reported appropriately as delineated in Section 13.2. In addition, postoperative high IOP or corneal edema (grade 3) presented

Document: TDOC-0050176 Version: 2.0; Effective; CURRENT

Status: Effective Page 51 of 75

persistently from 1 day to 1 month postoperative should be considered as a serious adverse event.

An adverse device effect (ADE) is an AE related to the use of an investigational product (test or control article). This definition includes AEs resulting from insufficient or inadequate instructions for use, deployment, implantation, installation, or operation; any malfunction; and use error or intentional misuse of the test article or control article.

